12.0 Direct Access to Source Documents

Source data includes all information, original records of clinical findings, observations, or other activities in the clinical trial necessary for the reconstruction and evaluation of the trial. Source data are contained in source documents. Examples of these include but are not limited to: hospital records, clinical and office charts, laboratory notes, subjects' diaries or evaluation checklists, pharmacy dispensing records, recorded data from automated instruments, photographs,

13.0 Quality Control and Quality Assurance

A site visit will be held prior to initiation of subject enrollment. The protocol, CRFs, study drug supplies, and relevant procedures will be explained in detail at the site visit.

Subsequent to subject enrollment, a study site monitor from JD or its designees will review the CRFs and source documents to ensure that the study is conducted according to the protocol and GCP/ICH guidelines.

To ensure compliance with GCP/ICH guidelines and all applicable regulatory requirements, DR or its designee may conduct a quality assurance audit. Regulatory agencies may also conduct a regulatory inspection of this study. Such audits or inspections can occur at any time during or after completion of the study. If audits or inspections occur, the Investigator and the Institution agree to allow the auditor/inspector direct access to all relevant documents and to allocate his/her time and the time of his/her staff to the auditor/inspector to discuss findings and any relevant issues.

14.0 Ethics

This study will be conducted in accordance with local regulations, GCP, ICH guidelines and, where applicable, the Declaration of Helsinki. The Investigator at each site will be responsible for the overall conduct of the clinical trial for the site and will be responsible for ensuring the trial is conducted according to the protocol and all regulatory requirements and IRB/EC regulations.

15.0 Subject Informed Consent

Subjects (or their legal guardian) will sign written informed consent document. A copy of the document is attached.

16.0 Institutional Review

The protocol and informed consent form for the study must be approved by an appropriately constituted IRB as defined by local requirements. The list of the IRB voting members, their titles and/or occupations, and their institutional affiliations and/or the IRB general assurance number, if applicable, must be submitted to the Sponsor or its designee prior to shipment of study drug to the investigator.

A copy of the Letter of the Approval from the IRB which also contains the study's protocol title, number, and protocol version date, must be received by JD or (DR) or its designee prior to shipment of drug supplies to the Investigator.

Significant changes to the protocol by JD must also be approved by the IRB and documentation of this approval must be submitted to JD or its designee prior to implementation of any changes. Records of IRB annual review, if applicable, and approval of all documents pertaining to this study must be sent to DR or his designee and kept on file by the Investigator. These documents are subject to regulatory authority or the Sponsor or its designee inspection at any time during the study.

Periodic status reports and adverse drug events must be submitted to the IRB according to the IRB's reporting requirements. The IRB must also be notified of completion of the study and a final report must be submitted to the IRB in accordance with the IRB's reporting requirements. A copy of these reports should be sent to DR or his designee. The

Investigator must maintain an accurate and complete record of all communication, reports and submissions to the IRB.

17.0 General Information

All study records including CRFs, signed Form FDA 1572, originals of test results, informed consent forms, IRB approval letters, correspondence, and all other documents pertaining to the conduct of the study must be kept on file by the Investigator.

Changes to the protocol can be made only by written amendment agreed upon by EW and the Investigator. The IRB must be informed of all changes and must approve all changes that may increase risk to the subjects.

A new FDA 1752 form must be prepared and signed for any of the following circumstances: if there is any addition or name/address changes of the Investigator, a sub-Investigator, laboratory, facilities or IRB. This form and a copy of any additional CVs, laboratory license and certificates, and/or IRB membership list/assurance number, if applicable, must be sent to JD or its designee. A copy must also be retained in the Investigator's file. JD or its designee must be notified, in writing, when an Investigator leaves the institution where the study has been conducted. The Investigator must assign a designee to assume his/her study-related responsibilities.

18.0 Data Handling and Record Keeping

18.1 Confidentiality

The sponsor (DR) will preserve the confidentiality of all subjects taking part in this trial. The data in this trial may be used in company publications and regulatory submissions. Information about study subjects will be kept confidential in accordance with guidelines established by the HIPPA.

18.2 Case Report Forms

The sponsor (DR) will provide CRF's for each subject. Each subject will be identified by study identification number and subject's initials. All data reported on CRFs will be supported by source documents. The source documents must be made available to the Sponsor clinical monitors during scheduled monitoring visits, auditors during any audits requested by the Sponsor and to regulatory agencies during inspections. When a subject discontinues the study, the CRF must be completed in a timely manner and signed by the Investigator.

18.3 Record Keeping

All study records are subject to inspection by regulatory agencies or the Sponsor or the Sponsors designees at any time. Records must be kept for two years following written notification by the Sponsor of either regulatory approval or discontinuation of the development program.

18.4 Financial

As required by US Federal Regulation 21 CFR 54, each listed investigator who is involved in the treatment or evaluation of research subjects must disclose certain

financial arrangements with the Sponsor. To ensure compliance, each investigator listed on Form FDA 1572 must complete a financial disclosure form prior to the shipment of study drug and one year after the completion of the study. If any relevant changes in this information occur during this interval, a new or updated financial disclosure must be provided.

18.5 Publication

The first publication or disclosure of study results shall be a publication or disclosure coordinated by the Sponsor. Thereafter, all subsequent publications will reference the original publication(s).

References

1. Mahajan VM. Acute bacterial infections of the eye: their aetiology and treatment. *Br J Ophthalmol* 1983;**67**:191– 4.
3. Rietveld RP, van Weert HC, ter Riet G, Bindels PJ. Diagnostic impact of signs and symptoms in acute infectious conjunctivitis: systematic literature search. *BMJ* 2003;**327**:789.
4. Nash, EA, et. al. Patterns of emergency department visits for disorders of the eye and ocular adnexa *Arch Ophthalmol*, 1998; **116**: 1222-1226.
5. Saitoh-Inagawa W. et. al. Ten years' surveillance of viral conjunctivitis in Sapporo, Japan. *Graefes Archive for Clinical & Experimental Ophthalmolog.*, 1999; **237**:35-8.
6. Ishii K. et al. Comparative studies on aetiology and epidemiology of viral conjunctivitis in three countries of East Asia--Japan, Taiwan and South Korea. *Int Journal of Epidemiology* 1987; **16**: 98-103.
7. Aoki, K. et. al. A twenty-one year surveillance of Adenoviral Conjunctivitis in Sapporo, Japan.*Int Ophthalmol Clinics*. 2002; **42**:49-54.
8. Heggie, AD. Incidence and etiology of conjunctivitis in Navy recruits. *Mil Med*. 1990; **155**: 1-3.
9. Shields, T, et. al. A comparison of eye problems in primary care and ophthalmology practices, *Family Medicine*. 1991; **23**: 544-6.
10. Kilchington, PR et. al. Use of polymerase chain amplification reaction for the detection of adenoviruses in ocular swab specimens. *Invest Ophthalmol Vis Sci* 1994 **35**(12):4126-34.

Statistical Analysis Plan

Statistical and Analytic Plans

Chi-Square tests of homogeneity or Fisher exact tests (depending on validity of normality assumptions) were performed to assess if the distribution of the categorical outcome of clinical cure (i.e. score of zero on both conjunctival injection and conjunctival discharge) varied by treatment with either SCH-1 or placebo.

Descriptive statistics (i.e. mean and standard deviations [SD] for normally distributed data, median with interquartile ranges [IQR] for non-normally distributed data) were calculated for all relevant measures. Percentage breakdowns will be used for categorical variables (ie: gender, age). All P-Values will be two-sided with statistical significance evaluated at the 0.05 alpha level.

All analyses were performed in SAS Version 9.4 (SAS Institute, Inc. Cary, NC).

Determination of Sample Size

The determination of sample size was derived from clinical experience, in which we expected the clinical cure rates at day 5 to be approximately 20% and 80 % in the placebo and SCH-1 groups respectively. A sample of 15 patients per group will yield 87% power to detect a difference between 20% and 80%, based on a Fisher's exact test with a 0.05 significance level.

Changes in the Conduct of the Study or Planned Analyses

There were no changes in the conduct of the study or planned analysis.

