Assessment of Safety	
 Incidence of SPK at day 1 Incidence of SPK at Day 5 Intraocular pressure at Day 5 
VA loss of 4 or greater lines on Snellen VA Chart

Interim Analysis and Safety Monitoring	
 Safety data will be reviewed by [name], Medical Monitor and Sponsor. A summary report of the safety points will be created every 3 months, as well as the end of the study, and reported to the IRB.
Statistical Analysis	
The statistical analysis will evaluate: 1) The overall clinical success rate defined as the percentage of study participants achieving a clinical cure by Day 5 or an overall decrease in the sum of both grades by 3; 2) Microbiological cure rate defined as the percentage of study participants who demonstrate elimination of pre-treatment pathogen(s) by the Day 5 TOC exam.
 
A statistical difference in clinical cure rate will be defined where the 95% confidence limit for the difference in the two study groups (SCH1 vs. Placebo) is greater than (+/-)15%.
 
All data will be examined employing an “Intent to Treat” analysis for all patients. Mean outcome variables in the two study groups will be compared. Statistical means between both study groups will be analyzed by both parametric and non-parametric tests to allow for deviations of data from normal distributions.

Schedule of Visits and Assessments

	Screen / Visit 1	Visit 2	Visit 3
	Day 1	Day 3	Day 5
General Exams			
Informed consent	x		
Inclusion/exclusion criteria	x		
Medical history	x		
Vital signs	x		x
Physical Exam	x		
Patient comfort exam	x	x	x
AE assessment	x	x	x
Current meds	x	x	x
Ophthalmic exams			
BCVA	x		x
Visual acuity	x	x	x
Anterior segment slit lamp exam and tonometry	x	x	x
Dilated fundus exam	x		x

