5.1 Randomization and Masking

Approximately 30 patients will be randomized in a 1:1 ratio to either SCH1 or placebo. Randomization will be administered through “block randomization” (blocks of 4). The code will be kept by DR, who will not be involved in examining or grading patients.

Each investigator will receive a sealed envelope containing the description of the study medication assigned to each patient number. Investigators will be instructed not to open the envelope unless a medical emergency requires identification of the study medication.

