7.2 Study Procedures/Assessments

The second visit has a +/- 1 day window. The third visit has a +/-1 day window.

Visit 1

Perform the following activities on Visit 1 (baseline)

- Review

- BCVA

- SLE and tonometry

- DFE

- Grading of injection / discharge

- Dispense study medication

Visit 2

Perform the following activities on Visit 2

- Record AEs

- Review of current medications

- Visual acuity

- SLE

- Grading of injection / discharge

Visit 3

Perform the following activities on Visit 3

- Record AEs

- Review of current medications

- Visual acuity

SLE
Grading of injection / discharge
DFE

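### No planned analysis adjusts for the baseline injection and discharge grades, and the comparison of means names neither its outcome nor its governing test

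*Combined protocol and SAP*

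**What the plan says.** - **SAP, Statistical and Analytic Plans.** Clinical cure (zero on both signs) is compared between arms by "Chi-Square tests of homogeneity or Fisher exact tests". No covariate or stratum is named. Means, medians and percentages appear only as descriptive statistics. A general rule follows: "All P-Values will be two-sided with statistical significance evaluated at the 0.05 alpha level".
- **Protocol synopsis, Statistical Analysis.** "Mean outcome variables in the two study groups will be compared", and these are to be "analyzed by both parametric and non-parametric tests". The stated reason is possible departure from normality. The outcomes, the visit, the governing test and any covariate are left open.
- **Protocol section 7.2.** "Grading of injection / discharge" is listed at Visits 1, 2 and 3, and at Visit 1 it comes before study medication is dispensed. Each sign is scored 0-3, so every patient has a baseline sum and, if seen, a Day 5 sum.
- **Protocol section 5.1.** "Approximately 30 patients will be randomized in a 1:1 ratio to either SCH1 or placebo", in blocks of 4. No stratification by severity is mentioned.
- **SAP, Determination of Sample Size.** The trial is sized on "clinical cure rates at day 5 to be approximately 20% and 80 % in the placebo and SCH-1 groups respectively", with 15 per group, Fisher's exact test and 87% power.

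**The concern.** The starting grade affects what a patient can achieve. Entry requires only grade 1 on each sign. A patient entering at 1+1 has a sum of 2, cannot fall by 3, and can succeed only by reaching 0/0. A patient entering at 3+3 can succeed with a residual sum of 3. The Day 5 sum may well depend on the starting sum too. With about 15 per arm and no stratification, the arms can differ in severity by chance, and no planned analysis accounts for that.

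The comparison of means has a second weakness. It will produce two p-values per outcome, both read at 0.05. If they fall on opposite sides of 0.05, the plan does not say which one counts. At stake are the precision and the clear reading of the supporting evidence in a 30-patient trial.

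**Working it through.** **1. The plan's own figure.** Inputs (SAP): 15 per arm, 20% versus 80%, two-sided 0.05, Fisher's exact test. Power is the sum over a, b = 0..15 of Bin(a; 15, 0.2) × Bin(b; 15, 0.8), counting tables with Fisher p ≤ 0.05. The result is 0.872, which agrees with 87%. The stated power does not rely on baseline adjustment.

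**2. Where the baseline grade enters the plan.**

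| Planned analysis | Uses baseline grade? | Adjusts for it? |
|---|---|---|
| Cure, 0/0 (SAP) | No | No |
| Cure or fall of 3 in the sum (synopsis; section 4.1) | Yes, to define success | No |
| Mean outcomes (synopsis) | Not stated | No |

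**3. Chance imbalance.** Assume that 15 of 30 patients count as severe; the documents give no distribution. The number in one arm is hypergeometric.
- P(7 or 8) = 2 × C(15,7)² / C(30,15) = 2 × 6435² / 155,117,520 = 0.534, so P(arms differ by 3 or more) = 0.466.
- P(6 or 9) = 2 × 5005² / 155,117,520 = 0.323, so P(differ by 5 or more) = 0.466 - 0.323 = 0.143.

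**4. Precision.** For baseline-outcome correlation ρ (assumed), adjustment multiplies the variance of a mean difference by about (1 - ρ²) × (1 + 1/26). The second factor is the cost of one extra parameter at N = 30.

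| ρ | 1 - ρ² | With the cost |
|---|---|---|
| 0 | 1.00 | 1.04 |
| 0.3 | 0.91 | 0.95 |
| 0.5 | 0.75 | 0.78 |
| 0.7 | 0.51 | 0.53 |

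**5. Power, 15 per arm.** The documents give no SD, so the closest anchor is the SAP's cure rates. In simulated integer sums of 0-6 with 80%/20% cure, and type I error about 5%:

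| Dependence on baseline (assumed) | t-test | ANCOVA | Change, points |
|---|---|---|---|
| None | 82% | 81% | -1 |
| Moderate | 72% | 75% | +3 |
| Strong | 58% | 66% | +8 |

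A second simulation used uniform baseline grades and set 80%/20% cure at a baseline sum of 4. It gave 86% for both methods with no dependence, and gains of about 5 and 11 points when the log-odds of cure changed by 0.5 and 1.0 per baseline point.

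Fixing a 1-SD effect instead gives a similar picture, but that effect size has no source in the documents. At ρ = 0, 0.3, 0.5 and 0.6:
- Rounded, bounded sums: t-test about 72%; ANCOVA 71%, 74%, 80% and 85%.
- Unbounded normal data: t-test about 75%; ANCOVA 74%, 78%, 85% and 90%.

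**6. Choosing between two tests.** 20,000 null trials per shape, 15 versus 15, so the Monte Carlo standard error near 5% is √(0.05 × 0.95 / 20,000) = 0.15 points:

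| Outcome shape | t-test | Rank test | Smaller p-value |
|---|---|---|---|
| Normal | 5.0% | 4.4% | 5.8% |
| Lognormal | 3.5% | 4.4% | 5.6% |
| 0-6 sum | 5.0% | 4.5% | 5.4% |
| 1-5 score | 5.2% | 4.8% | 5.9% |

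**The case against.** Several stronger readings are tempting, and the documents do not support them.

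- *That the baseline grade is not used at all.* A fall of 3 in the sum is computed from baseline and is part of the protocol's primary endpoint. Only adjustment and stratification are absent.
- *That the primary test is biased or underpowered.* Randomization keeps an unadjusted test valid; chance imbalance costs precision. The 87% reproduces without adjustment. Differing by 3 or more includes a 9 versus 6 split, which is ordinary chance variation.
- *That having two tests seriously inflates type I error.* The excess is under 1 percentage point, on an analysis that does not set the sample size.

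Other objections have some weight. The SAP contains no between-arm test of means; that sentence is only in the synopsis, so the fix adds an analysis to the SAP. The unnamed outcomes might include the 1-5 symptom score, which has no stated pre-treatment value, so the outcome must be named before a covariate can be chosen. The synopsis also gives a sensible motive for running both kinds of test, but a motive does not tell the reader which result governs.

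The size of the gain is unsettled. With no association there is a small loss. If most treated patients reach zero, the sum will be far from normal. The power figures compare ANCOVA with the t-test only and do not show that it beats a rank test, which can do better when one arm piles up at zero. That is a reason to report a rank-based version, and not a reason to leave the choice open.

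**Conclusion.** The point holds in a limited form. No planned analysis adjusts for or stratifies by a baseline grade that is already collected, and the comparison of means has neither a named outcome nor a governing test. The SAP does not resolve either gap.

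At the SAP's cure rates, ANCOVA in place of the t-test is worth between about -1 point of power and roughly +3 to +11 points. This rests on an assumed association between baseline and Day 5 that the documents do not give. The effect of test choice on type I error is small, at about 5.4%-5.9%. The more practical cost is that a split result would have no prespecified reading. This is a cheap improvement to a supporting analysis. It does not correct an error in the primary test.

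**What to change.** Keep Fisher's exact test on cure, on which the sample size rests, as the primary test. In the synopsis and the SAP, replace the two-test comparison of means with wording such as:

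> The Day 5 injection-plus-discharge sum in the study eye will be compared between arms by analysis of covariance with treatment and the Visit 1 sum as terms, reporting the adjusted difference and its 95% confidence interval. A rank-based version is a sensitivity analysis and does not replace this result.

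If other mean outcomes are intended, such as the symptom score, list each with its visit and one governing method.

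The cost is two sentences and one degree of freedom, with no new data, visits or patients. The model assumes approximate normality for a 0-6 sum, and the rank-based version covers that. Parts of the SAP are written in the past tense. If treatment codes have already been broken, the adjusted analysis should be reported as post hoc.

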4.0 Endpoints

4.1 Primary Endpoints

The primary endpoint will be the achievement of a clinical cure defined as a rating of 0/3 for bulbar conjunctival injection and 0/3 for conjunctival exudates/discharge or clinical success defined as an overall decrease by 3 in the sum of both scores.

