9.1 Graded Measure of Conjunctival Discharge / Exudates

A three-point rating scale (0=absent, 1=mild, 2=moderate, 3=severe) will be employed to grade conjunctival discharge/exudates. Clinical efficacy will be defined as reduction in score by 2 grades (i.e. 3->1, 2->0) or a score of 0.

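### The SAP tests and powers clinical cure alone, while the protocol's primary endpoint is cure or a 3-point fall, and the SAP states that nothing changed

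*Combined protocol and SAP*

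**What the plan says.** **Protocol, Section 4.1.** "The primary endpoint will be the achievement of a clinical cure defined as a rating of 0/3 for bulbar conjunctival injection", with grade 0 also required for discharge, "or clinical success defined as an overall decrease by 3 in the sum of both scores". The synopsis endpoint row says the same, and Section 9.2 defines clinical efficacy in matching terms. Section 4.1 names no day.

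**Protocol synopsis, Statistical Analysis row.** The first rate to be evaluated is the composite: "percentage of study participants achieving a clinical cure by Day 5 or an overall decrease in the sum of both grades by 3". The decision rule that follows is worded for a different quantity: "A statistical difference in clinical cure rate will be defined where the 95% confidence limit for the difference in the two study groups".

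**SAP, Statistical and Analytic Plans.** The only outcome given an inferential test, chi-square or Fisher exact, is whether "clinical cure (i.e. score of zero on both conjunctival injection and conjunctival discharge) varied by treatment". The 3-point fall appears nowhere in the SAP.

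**SAP, Determination of Sample Size.** Power of 87% with 15 per group, for cure rates of 20% on placebo and 80% on SCH-1 at day 5, by Fisher's exact test at 0.05.

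**SAP, closing statement.** "There were no changes in the conduct of the study or planned analysis".

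**The concern.** A reader following the SAP would never test the endpoint that the protocol calls primary. The outcome that is tested has a different response rate, and the stated power belongs to it. Two outcomes therefore have a claim to be the headline result, and the documents do not say which one decides the trial. The statement that nothing changed hides the difference from anyone who reads the SAP alone.

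The time point is loose as well. Section 4.1 gives none, the synopsis counts cure by Day 5, and the SAP's sample-size text places it at day 5. With 15 per arm, one patient classified differently moves an arm's rate by 1/15 = 6.7 percentage points.

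**Working it through.** **1. Can the endpoints differ?** Let S be the baseline sum of the two grades and F the sum at follow-up. Cure means F = 0. Success without cure needs F ≥ 1 and S − F ≥ 3, hence S ≥ 4.

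- S of 2 or 3: a 3-point fall is possible only by reaching 0, so the endpoints coincide.
- S of 4, 5 or 6: they can differ. For example, 2+2 to 1+0 (sum 4 to 1) and 3+3 to 2+1 (sum 6 to 3) are successes under Section 4.1 and failures under the SAP.

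The number of patients affected cannot be derived. The documents give no baseline grade distribution, and the entry rule is unclear. The synopsis inclusion list asks for an injection grade of 1, its target-population row asks for at least 1, and Section 6.1 sets no grade threshold. If both signs must be at least 1, there are 9 possible grade pairs and 6 have S ≥ 4. If injection must be exactly 1, the pairs are 1+1, 1+2 and 1+3, and only the last has S ≥ 4. These are counts of grade pairs, not of patients.

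**2. Reproduce the stated power.** Inputs from the SAP: n = 15 per arm, rates 0.20 and 0.80, two-sided Fisher test, alpha 0.05.

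Power = Σ over a, b = 0 to 15 of Bin(a; 15, p0) × Bin(b; 15, p1) × 1[Fisher p(a, b) ≤ 0.05]

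With p0 = 0.20 and p1 = 0.80 this gives 0.872. The 87% is correct for cure.

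**3. Power for the composite.** The documents give no arm-level composite rates, so the rates below are assumptions. Each is the SAP's cure rate plus an assumed share of all patients in the arm who fall 3 points without cure.

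| Added, placebo | Added, SCH-1 | Composite rates | Fisher power, 15 per arm |
|---|---|---|---|
| 30 points | 0 | 50% vs 80% | 24.6% |
| 30 points | 10 points | 50% vs 90% | 53.6% |
| 15 points | 5 points | 35% vs 85% | 69.7% |
| 10 points | 5 points | 30% vs 85% | 79.6% |
| 10 points | 10 points | 30% vs 90% | 89.4% |
| 0 | 10 points | 20% vs 90% | 97.5% |
| 0 | 15 points | 20% vs 95% | 99.4% |

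Power can move either way from 87%. Section 11 claims power above 80% for clinical success, but with 30 patients in each group and no arm-level rates, so it does not supply a figure for 15 per arm.

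**4. How often would the two tests disagree?** This was simulated with 400,000 trials per scenario and cure held at 20% versus 80%. The Fisher tests of cure and of the composite reach different conclusions in about 13% of trials when the composite is 30% vs 85%, 21% at 40% vs 90%, and 37% at 50% vs 90%.

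**5. False positives if either endpoint could be claimed.** Under six assumed null scenarios, the chance that at least one test is significant is about 2.9% to 3.2% with Fisher, against 1.6% to 1.7% for one endpoint. With the uncorrected chi-square it is about 8.3% to 9.3%.

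**The case against.** The SAP never labels cure as primary, and the synopsis words its decision rule for the cure rate, so testing cure has a footing in the protocol. Both points are accurate. They place the start of the conflict inside the protocol but do not remove it: cure is the only outcome the SAP tests and the only basis for its sample size, while Section 4.1 and the synopsis endpoint row are unambiguous.

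Cure is also the stricter outcome, since every cure is a composite success, so the SAP might be thought conservative. That does not follow. Which endpoint shows the larger treatment difference depends on the partial-response rates in each arm, which are unknown.

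Three stronger readings are tempting and are not supported:

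- *The switch inflates type I error above 5%.* With Fisher, a free choice between the endpoints stayed below 5% in every scenario tried. Only the uncorrected chi-square exceeded it. The SAP permits either test, and nothing shows that such a choice was made.
- *The SAP was written after unmasking.* It mixes past and future tense, but the documents give no date for it and do not establish when it was drafted.
- *Section 9.1 is a rival primary endpoint.* Its rule, "Clinical efficacy will be defined as reduction in score by 2 grades (i.e. 3->1, 2->0) or a score of 0", stands under the discharge heading and is not called primary. It needs aligning, but it is a definition for one sign.

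**Conclusion.** The mismatch is in the text and needs no assumption: the protocol's primary endpoint is cure or a 3-point fall, the SAP tests and powers cure alone, and its statement of no changes is wrong when set against Section 4.1. The primary analysis is therefore not fixed across the two documents, and the time point is not fixed either.

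The size of the consequence is uncertain. It depends on how many patients enter with a summed grade of 4 or more and on partial-response rates that the documents do not give. A reader might infer that moving to the composite costs power. The documents do not support a direction: over the assumed rates, power at 15 per arm runs from 25% to 99%. The supportable statement is that the 87% does not describe the protocol's primary endpoint.

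**What to change.** - Make the Section 4.1 composite the SAP's primary analysis, in the study eye as designated in Section 4.3, at the Day 5 visit.
- State whether a decrease by 3 means at least 3. If it meant exactly 3, a patient going from 3+3 to 1+1 (a fall of 4, not cured) would fail.
- Make cure-only a named secondary endpoint.
- State that the 87% applies to cure at 20% versus 80%, and give power for the composite under stated assumed rates, with a range.
- Align the synopsis Statistical Analysis row (the list of rates and the decision rule) and Sections 9.1 and 9.2 to this wording. Reconcile the synopsis entry lines on injection grade, since they determine how often the endpoints can differ.
- Replace the no-changes statement with a disclosure of the difference between protocol and SAP.

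Cure-only may be made primary instead, but only by amending Section 4.1 before unmasking. If the data are already unmasked, report the Section 4.1 endpoint as primary with cure alongside.

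The cost is wording plus one power calculation. The downside is that cure-only loses its place as the sole tested endpoint, and the stated power may become less favourable.

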5.0 Trial Design

This is a Phase II single-center, double-masked, placebo controlled, randomized study of SCH1 for the treatment of infectious conjunctivitis. Approximately 30 subjects will be enrolled, who will be randomized in a 1:1 ratio between SCH1 and placebo. Subjects will be assessed at day 1, day 3, and day 5 for efficacy and safety.

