11.0 Statistical Considerations

The clinical success rate is expected 50%-75% higher in the treatment group than in the placebo group. The microbiological cure rate is expected to be 60%-80% higher in the treatment drug arm compared to the placebo arm. Based on these estimates of efficacy, statistical and clinical significance will be demonstrable with 30 patients in each group to assure an outcome analysis with a power of >80% to detect the difference between the two groups at the 95% confidence interval.

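### The 87% power is computed for Fisher's exact test, but the SAP lets the analysis use chi-square or Fisher with no stated rule, so true error, power and some conclusions at 15 v 15 depend on an open choice; one prespecified exact unconditional test would close it

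*Combined protocol and SAP*

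**What the plan says.** Under Determination of Sample Size, the SAP gives the assumed rates: "we expected the clinical cure rates at day 5 to be approximately 20% and 80 % in the placebo and SCH-1 groups respectively". It then says "A sample of 15 patients per group will yield 87% power to detect a difference between 20% and 80" (per cent), "based on a Fisher's exact test with a 0.05 significance level". Section 5.0 of the protocol has patients "randomized in a 1:1 ratio between SCH1 and placebo".

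Under Statistical and Analytic Plans, the test for clinical cure is not fixed: "Chi-Square tests of homogeneity or Fisher exact tests (depending on validity of normality assumptions) were performed". The same part adds: "All P-Values will be two-sided with statistical significance evaluated at the 0.05 alpha level". The documents give no criterion for the switch, do not say whether chi-square carries a continuity correction, and do not discuss the error rate that either test attains at this sample size.

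**The concern.** The power statement and the analysis statement do not describe the same procedure. Power is computed for Fisher alone, while the analysis may use chi-square. The switch depends on normality, which a yes/no outcome cannot have. The likeliest meaning is that the normal approximation to the test statistic is adequate, but no cut-off is given.

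With 15 per arm this matters, because the tests differ visibly. Fisher is very discrete and leaves much of the nominal 5% unused. Uncorrected chi-square can slightly exceed 5%. There is a band of plausible results in which one is significant and the other is not. A choice made after those results are seen could decide the trial's conclusion.

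**Working it through.** **Inputs.** 15 per arm, 20% v 80%, Fisher at 0.05, two-sided (SAP, Determination of Sample Size and Statistical and Analytic Plans); 1:1 allocation (protocol Section 5.0).

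**Method.** There are 16 × 16 = 256 possible tables (a cures of 15, b cures of 15).
- Power(p1, p2) = Σ over a, b of Bin(a; 15, p1) × Bin(b; 15, p2) × [1 if the test rejects, else 0].
- Maximum true size = the largest value of Power(p, p) over a fine grid of common cure rates p.
- Boschloo p-value = the maximum over p of the probability of a table whose two-sided Fisher p-value is no larger than the one observed.

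**1. The plan's own figure.** Fisher at 20% v 80% gives 87.2%, against 87% stated. It reproduces.

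**2. True size at nominal 0.05.**

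| Procedure | Tables rejected | Maximum true size |
|---|---|---|
| Fisher | 102 | 1.77% |
| Expected-count switch (assumed) | 114 | 4.28% |
| Boschloo | 122 | 4.33% |
| Uncorrected chi-square always | – | 5.50% |

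The switch row assumes chi-square when all expected counts are at least 5, otherwise Fisher. Boschloo's region contains all 102 Fisher tables plus 20 more (122 − 102), and every table that the switch rejects. At this sample size its power is therefore never below either.

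**3. Power (%).**

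| SCH-1 v placebo | Fisher | Boschloo | Boschloo − Fisher | Switch |
|---|---|---|---|---|
| 80 v 20 | 87.2 | 93.9 | 6.7 | 93.9 |
| 75 v 20 | 78.5 | 88.4 | 9.9 | 88.3 |
| 70 v 20 | 68.0 | 80.7 | 12.7 | 80.5 |
| 65 v 20 | 56.4 | 71.0 | 14.6 | 70.6 |
| 60 v 20 | 44.7 | 59.9 | 15.2 | 59.1 |
| 70 v 30 | 43.4 | 59.0 | 15.6 | 58.9 |
| 50 v 20 | 24.6 | 37.3 | 12.7 | 35.2 |
| 40 v 20 | 11.2 | 19.2 | 8.0 | 16.0 |
| 30 v 10 | 14.9 | 25.6 | 10.7 | 16.0 |

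At 20% v 80% the assumed switch would choose chi-square in 98.9% of trials, which is why its power is 93.9%. Chi-square used always gives 94.1%. At 30 v 10, where small expected counts send more tables to Fisher, Boschloo gains 25.6 − 16.0 = 9.6 points over the switch.

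**4. Results on which the tests disagree.**

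| Result | Fisher p | Chi-square p | Boschloo p |
|---|---|---|---|
| 8/15 v 2/15 | 0.0502 | 0.020 | 0.023 |
| 9/15 v 3/15 | 0.060 | 0.025 | 0.030 |
| 10/15 v 4/15 | 0.066 | 0.028 | 0.043 |

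Chi-square for 9/15 v 3/15: pooled rate 12/30 = 0.40; z = (9/15 − 3/15) / √(0.40 × 0.60 × 2/15) = 0.40 / √0.032 = 2.236; two-sided p = 0.025. The smallest expected count is 12/2 = 6.

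Fisher misses these tables because of discreteness. With 12 cures in total, its attainable two-sided p-values step from 0.0078 to 0.060, so nothing between 0.8% and 6% is available.

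**The case against.** The strongest reply is that the quoted sentence contains no error. The 87% is correct for the test it names, 0.05 is a nominal level, and a test whose true size lies below its nominal level is valid. The 87% already carries Fisher's conservatism and still exceeds the target above 80% in protocol Section 11.0. All of that stands. Preferring Boschloo to Fisher is, taken alone, an efficiency choice.

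A reader might go further and infer that the plan gives up 7 points of power at the planned effect and 13 to 16 points at every smaller one. The documents do not support that. The analysis paragraph does not commit to Fisher, and under the usual expected-count rule almost nothing is lost at the planned rates. On that rule, 8/15 v 2/15, 9/15 v 3/15 and 10/15 v 4/15 would all go to chi-square and be positive. Nor is the loss under Fisher uniform: it is 9.9 points at 75 v 20 and 8.0 at 40 v 20.

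Two further limits stand. The two-sided Boschloo p-value depends on convention: for 10/15 v 4/15, ordering by the two-sided Fisher p-value gives 0.043, while a common software routine gives 0.034, with the same decision. And much of the SAP is in the past tense; if results were already known when it was written, moving to a test that rejects more tables would be post hoc.

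The reply does not remove the gap itself. That the loss may or may not occur depending on an unstated rule is the point.

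**Conclusion.** The point holds as a gap in prespecification with an efficiency cost that depends on which test is used; it is not a numerical error.

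- If Fisher is used, true error is at most 1.8%, and power against Boschloo is 6.7 points lower at the planned rates and about 13 to 16 points lower at several differences of 30 to 50 points.
- If uncorrected chi-square is always used, true error can reach 5.5%.
- If the expected-count rule is meant, size is controlled (4.28%), but the power of the planned procedure is 93.9% rather than 87%. Boschloo then adds little at the planned rates and more at low cure rates.

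In every case the stated power and the stated analysis need to be made to match, and the disputed tables show that the choice can change the conclusion.

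The figures assume exactly 15 evaluable patients per arm, independent binomial outcomes and cure as the SAP defines it. They do not settle separate matters: the sample size in protocol Section 11.0 ("30 patients in each group to assure an outcome analysis with a power of >80" per cent), the 15% confidence-limit criterion in the synopsis, or the difference between the protocol's primary endpoint (cure or a 3-grade fall) and the SAP's cure-only outcome.

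**What to change.** If the data are still masked:
- Name one primary test of the cure proportions: Boschloo's exact unconditional test, two-sided, tables ordered by the two-sided Fisher p-value, alpha 0.05.
- Delete the chi-square/Fisher switch.
- Restate the sample-size sentence: 15 patients per group give about 94% power for 20% v 80% by Boschloo's test, with maximum type I error 4.3%.
- Report Fisher's p-value as a sensitivity result.

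If the data are already unmasked, leave the primary test unchanged, state which test was used and by what rule, and add Boschloo as a labelled sensitivity analysis.

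The cost is about two sentences of SAP text and a few lines of code, with no extra patients or procedures. The small downside is a less familiar test, whose ordering convention has to be written down.
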